#### **Blood Sampling and Handling**

Detailed instructions on how to draw and prepare serum samples for progesterone and estradiol analysis, and liver function analysis (Part 2 only) will be investigational center-specific and provided in the laboratory SOPs and/or Study Manual. Briefly, blood samples for progesterone and estradiol (up to 10 mL) will be collected via venipuncture, centrifuged, and then transferred into 2 aliquots. One aliquot will be sent to the investigational center laboratory for the same day testing; and the other one stored as a back-up sample at -20°C. Collection and movement of progesterone and estradiol samples will be recorded on appropriate study CRFs and/or tracking tools. In Part 2 blood samples for liver function analysis (up to 5 mL) will be collected via venipuncture, centrifuged and then transferred to one aliquot for analysis.

## 7. ASSESSMENT OF SAFETY

In this study, safety will be assessed by qualified study personnel by evaluating the following: vital signs (BP [systolic/diastolic], pulse, and respiration), body weight, adverse events, concomitant medication usage, changes in menstrual bleeding patterns, mood, liver function tests, occurrence of ISRs, and return to ovulation after 12 months after the study drug injection.

#### 7.1. Adverse Events

#### 7.1.1. Definition of an Adverse Event

An adverse event is any untoward medical occurrence in a subject administered a pharmaceutical product, regardless of whether it has a causal relationship with this treatment.

In this study, any adverse event occurring after signing the informed consent form should be recorded and reported as an adverse event.

An adverse event can, therefore, be any unfavorable and unintended medical condition (eg, physical sign, symptom, disease, or laboratory parameter) that develops or worsens in severity during the course of this study, whether or not considered related to the study drug. The worsening of a pre-existing condition will be considered an adverse event. Stable chronic conditions (such as arthritis) that are present before study entry and do not worsen during this study will not be considered adverse events. Irregular vaginal bleeding will not be recorded on the Adverse Event Form unless it requires medical intervention or meets the definition of a serious adverse event.

Accordingly, an adverse event can include any of the following:

- intercurrent illnesses
- physical injuries
- events possibly related to concomitant medication
- significant worsening (change in nature, severity, or frequency) of the disease under study or other pre-existing conditions (Note: A condition recorded as pre-existing that is intermittently symptomatic [eg, headache] and that occurs during this study should be recorded as an adverse event.)
- drug interactions
- events occurring during diagnostic procedures or during any washout phase of this study
- laboratory or diagnostic test abnormalities that result in the withdrawal of the subject from the study, are associated with clinical signs and symptoms or a serious adverse event, or require medical treatment or further diagnostic work-up, or are considered by the investigator to be clinically significant. (Note: Abnormal laboratory test results at the screening visit that preclude a subject from entering the study or receiving study treatment are not considered adverse events.)

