### **Menstrual Changes**

Most women using Depo-Provera CI or Depo-subQ 104 experience disruption of menstrual bleeding patterns. Altered menstrual bleeding patterns include amenorrhea, irregular or unpredictable bleeding or spotting, prolonged spotting or bleeding, and heavy bleeding. As women continue using Depo-Provera CI or Depo-subQ 104, fewer experience irregular menstrual bleeding and more experience amenorrhea. In 3 contraception trials, 39.0% of women experienced amenorrhea during month 6, and 56.5% experienced amenorrhea during month 12 (Depo-subQ 104 US Prescribing Information 2016). The effect on bleeding pattern of a single subcutaneous administration of TV-46046 has not been clinically tested. Women with

unexplained vaginal bleeding or anemia (hemoglobin <10.5 g/dL) will not be eligible for the study. Changes in menstrual bleeding patterns and its acceptability will be evaluated at specified study visits. For details, see the Study Procedures and Assessments table (Table 1).

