# 7.4. Clinical Laboratory Tests

A clinical laboratory test for hemoglobin will be performed at the screening visit using the investigational center laboratory within 24 hours of blood collection. Liver function testing including, but not limited to, ALT and AST will be performed in Part 2 only by the investigational center laboratory at the screening visit, as well as at the month 3, month 7.5 and final visits. Detailed instructions on how to draw and prepare samples for liver function testing will be investigational center-specific and provided in the laboratory SOPs and/or Study Manual.

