8.2. Adverse Events

All AEs will be coded using MedDRA by preferred term and SOC. The number and percentage of participants experiencing AEs will be presented by treatment group: overall, by severity, relatedness to treatment, and according to whether or not the event had an onset date within 7.5 months of initiation of treatment. Serious adverse events and adverse events leading to withdrawal from the study will be summarized separately.

A listing of all AEs will include treatment group, verbatim AE description, preferred term and SOC, duration, relatedness to product, seriousness, severity, outcome, and whether withdrawal from the study occurred as a result of the AE. All relevant information on any deaths will be discussed in the subject narrative included in the clinical study report.

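### A woman who withdraws because of untreated, non-serious irregular bleeding can be missing from the table of adverse events leading to withdrawal, because the bleeding exemption has no withdrawal exception

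*Protocol*

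**What the plan says.** Protocol Section 7.1.1 says: "Irregular vaginal bleeding will not be recorded on the Adverse Event Form unless it requires medical intervention". The sentence goes on to a second exception, so that in full the exemption applies "unless it requires medical intervention or meets the definition of a serious adverse event". Those are the only two exceptions. The list of adverse-event types in the same section does use withdrawal as a trigger, but for another category: "laboratory or diagnostic test abnormalities that result in the withdrawal of the subject from the study".

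Protocol Section 1.4.2 names altered bleeding as an effect to expect with this class of product: "Altered menstrual bleeding patterns include amenorrhea, irregular or unpredictable bleeding or spotting, prolonged spotting or bleeding, and heavy bleeding".

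On reporting, SAP Section 8.2 says: "Serious adverse events and adverse events leading to withdrawal from the study will be summarized separately". Protocol Section 8.8.2 says the same. Neither brings in withdrawals from any source other than recorded adverse events.

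Two further rules bear on the case. Protocol Section 7.1.2 requires every adverse event to be entered on the case report form whatever its severity. Section 7.1.7 requires the adverse event form to be completed when a woman is withdrawn wholly or partly because of an adverse event.

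**The concern.** A table of adverse events leading to withdrawal is a natural place to look for how many women could not tolerate the product. For an injectable progestin expected to disturb bleeding in most users, bleeding is an obvious candidate reason for leaving. Under Section 7.1.1 as written, a woman who leaves because of irregular bleeding that was neither treated nor serious has nothing on the Adverse Event Form, and so nothing to count in that table.

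The groups are very small, so one misplaced withdrawal changes how a group looks. The text can also be read in two ways, so two sites, or two staff members at one site, could handle identical cases differently.

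**Working it through.** The plan gives no figure to reproduce. The check is mainly a comparison of rules, followed by arithmetic for scale.

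**Step 1. Follow one case through the rules.** Take a woman in Part 1 who leaves because of irregular bleeding, without medical intervention and without meeting a serious criterion.

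| Rule | Where | Result for her |
|---|---|---|
| Bleeding exemption | Protocol 7.1.1 | Not on the Adverse Event Form; neither exception applies |
| Withdrawal as a trigger | Protocol 7.1.1, laboratory item | Does not apply; it covers laboratory and diagnostic abnormalities |
| Adverse event form at withdrawal | Protocol 7.1.7 | Applies only if her bleeding counts as an adverse event |
| Adverse events leading to withdrawal | Protocol 8.8.2, SAP 8.2 | Absent, because the table is built from adverse events |
| Reason for discontinuation | Protocol 3.12, 4.4, 8.4.1; SAP 5.2 | Present, but no reason categories are listed |
| Bleeding interview at final visit | Protocol 3.14.4.1, 7.8; SAP 8.5 | Present if the final visit is done; not cross-tabulated with withdrawal |
| Acceptability interview at final visit | Protocol 3.14.4.1; SAP 9 | Present if the final visit is done; not cross-tabulated with withdrawal |

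**Step 2. Test the other reading.** Section 7.1.1 says that such bleeding is not recorded on the form. It does not say that the bleeding is not an adverse event. With 7.1.2 and 7.1.7, a site could decide that bleeding bad enough to make a woman leave is an adverse event and complete the form. The specific exemption points one way and the general withdrawal rule the other, and nothing says which prevails.

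**Step 3. Scale for one woman.** Part 1 has six women per group, with 12 planned and up to 18 if the third group is enrolled.

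- One of 6 is 1/6 = 17%.
- One of 12 is 1/12 = 8%.
- One of 18 is 1/18 = 6%.

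Under the exemption, each would show as 0% in the adverse-event withdrawal table.

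**Step 4. Chance that it happens at all.** The documents give no rate for this kind of withdrawal, so the rate p is an assumption, shown over a range. The chance of at least one such woman among n is 1 − (1 − p)^n. For example, with n = 12 and p = 5%, it is 1 − 0.95^12 = 46%.

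| Assumed p | n = 12 | n = 18 |
|---|---|---|
| 1% | 11% | 17% |
| 2% | 22% | 31% |
| 5% | 46% | 60% |
| 10% | 72% | 85% |

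Part 2 was not implemented (SAP footnote 1 and Section 13.3), so larger numbers do not apply.

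**The case against.** The strongest reply is that this is deliberate routing and that nothing is lost. Bleeding change is a safety endpoint in its own right (Protocol 2.3.3). It is collected monthly in Part 1 and tabulated in SAP 8.5, including the number of women who ever report an unacceptable pattern. An early leaver should have the final visit where possible, with bleeding and acceptability interviews and an adverse-event inquiry. Her reason for leaving is recorded and tabulated. No document says that the adverse-event withdrawal table is the only place to look for tolerability-driven loss.

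Most of this stands, and it limits the point to one table. It does not remove the point. A disposition table with unspecified reason categories need not show bleeding separately. SAP 8.5 shows who had disturbed bleeding, not who left because of it.

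Three stronger readings are tempting, and the documents do not support them.

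- A reader might infer that all bleeding-related withdrawals vanish from the adverse-event tables. Treated or serious bleeding is recorded. The exemption also names irregular bleeding only, whereas Section 1.4.2 lists prolonged and heavy bleeding as separate items. Whether the exemption covers those is unclear; it cannot be assumed.
- A reader might infer that such a woman appears nowhere except as a reason for discontinuation. The final-visit interviews show otherwise, where that visit takes place.
- A reader might infer that anaemia would go undetected, because "A clinical laboratory test for hemoglobin will be performed at the screening visit using the investigational center laboratory" and no later test is scheduled. But Section 7.4, Table 1 and Table 2 agree on screening only, so there is no inconsistency to resolve. Diagnosed or symptomatic anaemia falls under the general adverse-event definition, and Section 3.14.5 allows further procedures at the investigator's discretion. The planned blood volume adds nothing to the argument: Table 2 labels its totals as maxima for a woman who does not ovulate before week 78, and the documents do not link that volume to a fall in haemoglobin.

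**Conclusion.** The point holds in a narrow form. The bleeding exemption in Protocol 7.1.1 has no withdrawal exception, while laboratory abnormalities in the same section do have a withdrawal trigger. The adverse-event withdrawal summary can therefore omit a woman who left because of untreated, non-serious irregular bleeding, and 7.1.7 leaves room for inconsistent coding.

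The effect is confined to that summary and to Part 1's 12 to 18 women. One case would turn 17% of a six-woman group into 0% there. Whether any such case occurred cannot be known from the documents, and the probabilities above rest entirely on assumed rates. The conclusion assumes that sites follow the specific exemption in 7.1.1 over the general rule in 7.1.7, and that no bleeding category is defined on forms outside these two documents.

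This is a recording and reporting gap that is worth closing because closing it costs almost nothing. It is not evidence that the bleeding risk is hidden, and no change to the laboratory schedule follows from it.

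**What to change.** **Recording rule (Protocol 7.1.1).** Add a third exception between the existing two, so that irregular bleeding also goes on the Adverse Event Form when it *is a reason (wholly or in part) for study withdrawal*. This matches the scope of 7.1.7 and removes the conflict between the two sections. It costs one phrase, with no new visit, test or form.

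**Reporting of Part 1 data already collected.** In the disposition table (SAP 5.2), show bleeding as its own discontinuation reason by treatment group, including zero counts. Under the table of adverse events leading to withdrawal (SAP 8.2), add a footnote giving the number of women who withdrew because of bleeding not recorded as an adverse event. The recorded reasons for discontinuation supply the information. The cost is one table row and one footnote.

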## 7.1.2. Recording and Reporting Adverse Events

For adverse event recording, the study period is defined for each subject as that time period from signature of the informed consent form to the end of the follow-up period.

All adverse events that occur during the defined study period must be recorded on the source documentation and transcribed onto the CRF, regardless of the severity of the event or judged relationship to the study drug. For serious adverse events, the Serious Adverse Event Form must also be completed and the serious adverse event must be reported immediately (see Section 7.1.5.3.1). The investigator does not need to actively monitor subjects for adverse events once the study has ended. Serious adverse events occurring to a subject after study discontinuation should be reported to the sponsor if the investigator becomes aware of them, following the procedures described in Section 7.1.5.3.1.

At each of the 3 scheduled follow-up visits, the investigator or designee must question the subject about adverse events by asking an open-ended question such as, "Have you had any unusual symptoms or medical problems since the last visit? If yes, please describe." All reported or observed signs and symptoms will be recorded individually, except when considered manifestations of a medical condition or disease state. A precise diagnosis will be recorded whenever possible. When such a diagnosis is made, all related signs, symptoms, and any test findings will be recorded collectively as a single diagnosis on the CRF and, if it is a serious adverse event, on the Serious Adverse Event Form. During frequent laboratory visits adverse events will not be actively solicited but will be documented if reported by the subject.

The clinical course of each adverse event will be monitored at suitable intervals until resolved or stabilized or returned to baseline, or until the subject is referred for continued care to a another healthcare professional, or until a determination of a cause unrelated to the study drug or study procedure is made.

The onset and end dates, duration (in case of adverse event duration of less than 24 hours), action taken regarding study drug, treatment administered, and outcome for each adverse event must be recorded on the source documentation and transcribed onto the CRF.

The relationship of each adverse event to study drug treatment and study procedures, and the severity and seriousness of each adverse event, as judged by the investigator, must be recorded as described below.

## 7.1.3. Severity of an Adverse Event

The severity of adverse events including ISRs and abnormal laboratory tests will be graded per the DAIDS Table for Grading Adult and Pediatric Adverse Events, Version 2.0, November 2014 (see Appendix A).

#### 7.1.4. Relationship of an Adverse Event to the Study Drug

The relationship of an adverse event to the study drug is characterized as follows and will be determined by Teva:

Term	Definition	Clarification
No reasonable possibility (not related)	This category applies to adverse events that, after careful consideration, are clearly due to extraneous causes (disease, environment, etc) or to adverse events that, after careful medical consideration at the time they are evaluated, are judged to be unrelated to the study drug.	
 
The relationship of an adverse event may be considered "no reasonable possibility" if it is clearly due to extraneous causes or if at least 2 of the following apply:
 
It does not follow a reasonable temporal sequence from the administration of the study drug.
 
It could readily have been produced by the subject's clinical state, environmental or toxic factors, or other modes of therapy administered to the subject.
 
It does not follow a known pattern of response to the study drug.
 
It does not reappear or worsen when the study drug is re-administered
 

Reasonable possibility (related)	This category applies to adverse events for which, after careful medical consideration at the time they are evaluated, a connection with the study drug administration cannot be ruled out with certainty.	
 
The relationship of an adverse event may be considered "reasonable possibility" if at least 2 of the following apply:
 
It follows a reasonable temporal sequence from administration of the study drug.
 
It cannot be reasonably explained by the known characteristics of the subject's clinical state, environmental or toxic factors or other modes of therapy administered to the subject.
 
It disappears or decreases on cessation or reduction in dose. There are important exceptions when an adverse event does not disappear upon discontinuation of the study drug, yet a drug relationship clearly exists.
 
It follows a known pattern of response to the study drug.
 

#### 7.1.5. Serious Adverse Events

#### 7.1.5.1. Definition of a Serious Adverse Event

A serious adverse event is an adverse event occurring at any dose that results in any of the following outcomes or actions:

- death
- a life-threatening adverse event (ie, the subject was at immediate risk of death from the event as it occurred); does not include an event that, had it occurred in a more severe form, might have caused death
- inpatient hospitalization or prolongation of existing hospitalization, which means that hospital inpatient admission and/or prolongation of hospital stay were required for treatment of an adverse event, or that they occurred as a consequence of the event.

- Hospitalizations scheduled prior to study entry or hospitalization for elective surgery of pre-existing condition will not be considered serious adverse events, unless there was worsening of the preexisting condition during the subject's participation in this study.
- a persistent or significant incapacity or substantial disruption of the ability to conduct normal life functions
- a congenital anomaly/birth defect
- important medical events that may not result in death, be life-threatening, or require hospitalization may be considered serious when, based upon appropriate medical judgment, they may jeopardize the patient or subject and may require medical or surgical intervention to prevent one of the outcomes listed in this definition.
- Examples of such events are intensive treatment in an emergency room or at home for allergic bronchospasm; blood dyscrasias or convulsions that do not result in hospitalization; or the development of drug dependency or drug abuse. Note: Any suspected transmission of an infectious agent via a medicinal product is considered an important medical event.

An adverse event that does not meet any of the criteria for seriousness listed above will be regarded as a nonserious adverse event, although it may nonetheless be severe (see Appendix A).

#### 7.1.5.2. Expectedness

A serious adverse event that is not included in the Adverse Reaction section of the relevant reference safety information by its specificity, severity, outcome, or frequency is considered an unexpected adverse event. The reference safety information (RSI) for this study is the current IB for TV-46046.

This is a Phase 1 clinical study; to date, expected adverse reactions have not been identified for the study drug. However, the composition of TV -46046 including the active product ingredient (API) is similar to the approved contraceptive injectables Depo-Provera CI and Depo-subQ 104. A serious adverse event that is not included in the Appendix A - Reference Safety Information for Expedited Reporting Purposes in the IB is considered an unexpected adverse event.

Teva's Pharmacovigilance Department will determine the expectedness for all serious adverse events.

For the purpose of suspected unexpected serious adverse reaction (SUSAR) reporting, the version of the IB at the time of occurrence of the SUSAR applies.

#### 7.1.5.3. Reporting a Serious Adverse Event

#### 7.1.5.3.1. Investigator Responsibility

To satisfy regulatory requirements, all serious adverse events (as described in Section 7.1.5.1) that occur during the study period (including the protocol-defined follow-up period, described in Section 7.1.2), regardless of judged relationship to treatment with the study drug, must be reported to the sponsor by the investigator. The event must be reported within 24 hours of when the investigator learns about it. Completing the serious adverse event form and reporting the

event must not be delayed, even if not all the information is available. The investigator does not need to actively monitor subjects for adverse events once this study has ended.

Serious adverse events occurring to a subject after the treatment of that subject has ended should be reported to the sponsor if the investigator becomes aware of them.

The serious adverse event form should be sent to the local safety officer (LSO) and FHI 360 (contact information is in the Clinical Study Personnel Contact Information section); the LSO will forward the report to the sponsor's Global Patient Safety & Pharmacovigilance Department.

The following information should be provided to record the event accurately and completely:

- study number
- investigator and investigational center identification
- participant number
- onset date and detailed description of adverse event
- investigator's assessment of the relationship of the adverse event to the study drug (no reasonable possibility, reasonable possibility)

Additional information may include the following:

- age and sex of subject
- date of study drug injection
- date and amount of last administered dose of study drug
- action taken
- outcome, if known
- severity
- explanation of assessment of relatedness
- concomitant therapy (including doses, routes, and regimens) and treatment of the event
- pertinent laboratory or other diagnostic test data
- medical history
- for an adverse event resulting in death:
  - cause of death (whether or not the death was related to study drug)
  - autopsy findings (if available)

Each report of a serious adverse event will be reviewed and evaluated by the investigator, the study medical monitor at FHI 360, and the sponsor to assess the nature of the event and the relationship of the event to the study drug, study procedures, and to underlying disease.

Additional information (follow-up) about any serious adverse event unavailable at the initial reporting should be forwarded by the investigational center within 24 hours of when it becomes known to the same address as the initial report.

For all countries, the sponsor's Global Patient Safety & Pharmacovigilance Department will distribute the Council for International Organizations of Medical Sciences (CIOMS) form/Extensible Markup Language (XML) file to the LSO and FHI 360 for local submission to the regulatory authorities, IEC/IRBs, and investigators, according to regulations. The investigator is responsible for ensuring that the IEC/IRB is also informed of the event, in accordance with national and local regulations.

Blinding will be maintained for the people who are involved directly in the study except for the pharmacist or other trained personnel\_administering the study drug injection. Therefore, in case of a SUSAR, only the LSO and FHI 360 medical monitor will receive the unblinded report for regulatory submission; the others will receive a blinded report.

Note: Although pregnancy is not a serious adverse event, the process for reporting a pregnancy is the same as that for reporting a serious adverse event, but using the pregnancy form (see Section 7.2).

